#### 7.1.3 Safety population

The safety population is defined as all patients receiving at least one treatment with the Carry Life® UF system.

#### 7.1.4 Per protocol treatments

Carry Life UF per protocol treatments are Carry Life UF treatments for which the Carry Life UF treatment with a treatment time of  $5 \pm 0.75$  hours and a total stop time during treatment of at most 30 min.

CAPD per protocol treatments are CAPD treatments with a total treatment time of  $5 \pm 0.75$  hours.

### 7.1.5 Randomization method

The randomization will occur after the in-clinic phase of the study, after the glucose dose the subject will use in the Carry Life® UF arm has been determined (refer to page 47 for a description of the dose determination). The randomization is being done to reduce any potential for bias based on subjects starting in the treatment or control arms. For each Carry Life® UF glucose dose (11 g/h and 15 g/h) the subjects will be randomized with an equal ratio (1:1) to start with either the control or the Carry Life® UF study arm. The randomization is based on block randomization using blocks of four, to ensure a balance between those who starts with control and those who starts with the Carry Life® UF arm. Subjects using the 11 g/h will be randomized to Group A or Group C. Subjects using the 15 g/h will be randomized to Group B or Group D. Group A and Group B will start with control. Group C and Group D will start with Carry Life UF. The randomization is a feature of the eCRF and will be managed centrally.

### 7.1.6 Statistical analysis of primary endpoint

The primary endpoint uses the UF measured per protocol at each efficacy evaluation treatment during the home treatment phase. Each subject is expected to have two efficacy evaluations per treatment arm. Subjects with one or more per protocol efficacy evaluations in each arm will be included in the primary endpoint analysis. The analysis will be performed for both the ITT and the PP population. Excluded subjects will be tabulated with narratives as to why they are missed efficacy evaluations.

For each subject, we use the mean  $UF_{CL}$  and the mean  $UF_{CAPD}$  for analysis. The mean difference (i.e., a paired comparison) between the UF achieved with the Carry Life® UF treatment and the UF achieved with the control CAPD dwell ( $UF_{CL}(n) - UF_{CAPD}$ ) will be calculated ( $UF_{diff}(n)$ ) with a 95% CI. A superiority (one sided t-test) test will be used to demonstrate that the Carry Life UF treatment is superior to the control with superiority margin of 250 ml. A superiority margin greater than 0 ml but less than 250 ml supports that the Carry Life® UF treatment increases UF as compared to the control, but at a level that may not be clinically significant.

For the primary endpoint analysis, the four groups (Group A, 11 g/h starting with control; Group B, 15 g/h starting with control, Group C, 11 g/h starting with Carry Life UF; Group D, 15 g/h starting with Carry Life UF) in the randomization scheme will be pooled. Control data generated from all four groups will be part of the control group and Carry Life UF data for both doses from all four groups will be part of the Carry Life UF group. This results in two final groups for primary endpoint analysis; control and Carry Life UF. Based on 1) prior pilot study results showing no significant difference between the doses and 2) our dose determination procedure, which assigns the glucose dose to be used by each subject based on the UF result in the in-clinic phase of the study, we expect the two Carry Life UF glucose dose groups to behave as a single population and be poolable for the purposes of the primary endpoint of the study. However, as part of our descriptive analysis, we intend to summarize the difference in UF volume between study arms for each Carry Life UF glucose dose as well as for different fill volumes.

The treatment performance for the primary objective will also be described based on demographic characteristics including age, gender, and ethnicity.

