### 3.7 EXPLORATORY STUDIES WITH MAINTAINED INTRAPERITONEAL GLUCOSE CONCENTRATION

Therapeutic concepts similar to the Carry Life® UF system such as continuous flow PD (CFPD) and steady concentration PD (SCPD) have been described in the literature. The features of CFPD are that the IP volume is fixed and that dialysate rapidly and continuously flows in and out of the peritoneal cavity, creating a stable IP glucose concentration. Studies performed with CFPD have demonstrated that CFPD results in a significantly higher UF volume compared to standard PD therapies.

In the study on adult PD patients by Freida *et al.* the UF volume in the PET (2.27% glucose), achieved 270 mL, whereas the mean UF in CFPD was 587 mL with a 1.36% PD solution. UF and net sodium removal extrapolated to eight hours of treatment was also much higher with CFPD (1175 mL UF; 212 mmol sodium removal) compared to 8 hours APD treatment APD (427 mL UF; 66 mmol sodium removal). Glucose absorption was not significantly different between the CFPD and APD session but the glucose UF efficiency (UF/absorbed glucose) was higher with the CFPD (33.5 mL/g) compared to APD (11.4 mL/g).

In a study by Pérez-Díaz a PD treatment concept close to that of the Carry Life® UF system was used. In the study a 50% glucose solution, at a dose of 20–30 g/h, was continuously administered to the IP fluid during four-hour dwells in PD patients with symptomatic fluid overload that could not be adequately treated with available PD methods. IP glucose concentrations at the end of the PD dwell was  $1.89 \pm 0.42\%$ . The highest IP glucose concentration was 2.7%. The treatment reversed all episodes of fluid overload, and serum glucose levels were stable and remained within safe levels during the study. The SCPD achieved high UF volumes in the four-hour sessions ( $653 \pm 363$  mL/4 h) and achieved twice the UF volume compared to the patients' PET tests ( $300 \pm 251$  mL/4 h) and

6 times that of their regular PD regime ( $100 \pm 123$  ml/4 h). The achieved UF volumes varied in the study participants, despite identical treatments being performed, which was partly explained by a correlation of UF to fluid overload. The conclusion of the Pérez-Díaz study was that SCPD may provide an effective and safe tool to manage UF in PD, opening new therapeutic possibilities to optimize and increase the flexibility of PD treatments.

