subject's standard diabetes management, will be evaluated daily by the clinic for at least three days, until judged clinically stable. Thereafter, blood glucose levels will be evaluated weekly by the clinic.

At the start of the second and third week of each study arm of the home treatment phase a nurse will contact the subject to check on clinical status, AEs, and Carry Life® UF device malfunctions. The clinical follow-up will include data on body weight and blood pressure, as well as a clinical assessment of volume status and clinical symptoms. These evaluations will also be performed at the end-of study arm visits.

Based on the clinical assessments throughout the study, the responsible physician will adjust the subject's PD prescription in order to maintain an adequate fluid balance according to clinical judgement and standard clinical practice. In the control arm, the glucose concentration of the PD dwells may be adjusted as required.

If a reduced peritoneal fluid removal is deemed necessary during the Carry Life® UF arm, the change in prescription shall be performed in the following order.

1. Reduce the glucose concentration of the CAPD dwells.
2. Reduce the frequency of the Carry Life® UF treatments.

When a Carry Life® UF treatment is removed from the prescription, a 2.27% glucose or a 1.36% glucose CAPD dwell will replace the Carry Life® UF treatment based on the clinical judgement of the responsible physician.

The Carry Life® UF treatment should be performed at least twice per week. If the subject requires a Carry Life® UF treatment frequency fewer than two days per week to avoid hypovolemia, the subject will be withdrawn from the study.

If an increased peritoneal fluid removal is deemed necessary during the Carry Life® UF arm, the change in prescription shall be performed in the following order:

1. Re-introduce the 2.27% glucose CAPD dwells that were reduced to 1.36% glucose (one at the time at a frequency indicated by the subject's clinical status).
2. When all 2.27% glucose dwells have been re-introduced, one additional Carry Life® UF treatment will be added weekly until the fluid removal is deemed sufficient. The added Carry Life® UF treatment will always replace a 2.27% glucose CAPD dwell.

All changes to the subject's PD prescription will be documented and the reason for the change specified.

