#### 6.2.6 Description of measures to minimize or avoid bias

The Sponsor will avoid improper influence on any parties participating in, or contributing to, the clinical investigation or the induction thereof. The selection and treatment of participants and evaluation of clinical investigation data are potential sources of bias. Methods that are incorporated within the clinical investigation design to minimize potential bias include, but are not limited to, screening participants to confirm eligibility with defined inclusion/exclusion criteria prior to enrolment; maintaining a log of all participants screened and enrolled; collecting demographics, medical history, and medications at baseline to later assess possible characteristics that may influence endpoints; standardizing data collection requirements and clinical investigation procedures; using standardized training materials for all study personnel; and by conducting regular monitoring visits to verify adherence to the CIP and source data.

As the clinical investigation involves the use of a medical device it is not possible to blind the investigational staff or the patients. Randomizing the order of the study arms in this cross-over study will minimize the risk that a general disease progress affects the outcome.

The UF volume result may be biased if the peritoneal drain is performed in different subject positions during the drain. During the efficacy evaluation days the subject will be instructed to perform the study drains in the sitting position.

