**6.4.3 Foreseeable factors that may compromise the outcome of the clinical investigation or the interpretation of results**

The present study is designed as a controlled, randomized, multicenter, crossover study. The UF outcome in PD is dependent on the peritoneal transfer (transport) characteristics. In order to evaluate the results based on the subject's transport characteristic a PET is performed to determine the patient's transport type. To reduce the impact of interpatient variability the study is designed as a crossover study where each patient will generate results from both study arm. The difference between treatment will be assessed by a paired analysis.

The determined UF is dependent on the actual UF as well as the dialysate volume remaining in the peritoneal cavity from the preceding dwell and after the recorded dwell. In order to account for that variability, the performance endpoints will be based on the average from two treatments in each arm.

In order to determine correct UF during PD it is very important to determine exactly the volume that is instilled into and drained from the peritoneal cavity. To ensure that the weighing of the solution bags and drain bags is performed correctly, detailed written weighing procedures will be used. Furthermore, weighing will be performed by trained study personnel or a Triomed representative during the efficacy evaluation treatments.

The study is randomized for in what arm to start the study in order to account for possible disease progression, e.g., a decline in RRF over the course of the study.

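### The primary paired t-test ignores the randomised order of arms, so a period effect biases the estimate when sequence counts differ and adds error variance at any split

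*Protocol*

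**What the plan says.** Protocol section 7.1.6 takes each subject's mean UF in each arm and forms the within-subject difference: "The mean difference (i.e., a paired comparison) between the UF achieved with the Carry Life® UF treatment and the UF achieved with the control CAPD". It then names the test: "A superiority (one sided t-test) test will be used to demonstrate that the Carry Life UF treatment is superior to the control", with a 250 ml margin. Groups A to D (two doses by two orders) are merged: "This results in two final groups for primary endpoint analysis; control and Carry Life UF". The reasons given for merging concern dose only: no significant dose difference in the pilot, and the dose-determination procedure. No reason is given for dropping order.

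Order is nevertheless what the trial randomises, within dose stratum. Section 7.1.5: "The randomization is based on block randomization using blocks of four, to ensure a balance between those who starts with control". Section 6.4.3 gives the purpose: "The study is randomized for in what arm to start the study in order to account for possible disease progression". Section 6.2.6 says the same: "Randomizing the order of the study arms in this cross-over study will minimize the risk that a general disease progress affects the outcome".

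Section 5.2 prints a different rejection rule. It has 2n in the standard error and 2n − 2 degrees of freedom, which is the form of a two-sequence crossover test with n subjects per sequence. Section 7.1.6 does not carry it over.

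**The concern.** Randomising order makes a period effect separable from the treatment effect, but only if the analysis uses the order. A one-sample t-test on pooled differences does not. It relies on the two sequences being equally represented among the analysed subjects, and it leaves the period effect in the error term even when they are.

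Equal representation is not assured. Blocks of four within two dose strata can end incomplete. About 25 are enrolled for 19 completers (section 6.3.1), and the analysis needs a per-protocol evaluation in each arm. Subjects can also be lost after randomisation, through failed device competency (6.2.4), too few device treatments per week (6.2.5) or peritonitis (6.3.2.1).

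The protocol's own example of change over time is residual renal function, but it also contains a possible route to peritoneal UF. Section 3.7 reports that UF varied between participants in a study of a similar method, "which was partly explained by a correlation of UF to fluid overload". Section 6.2.5 has the physician adjust each subject's "PD prescription in order to maintain an adequate fluid balance according to clinical judgement and standard clinical practice", so fluid status and prescription may move between periods. At stake are the precision of a small confirmatory comparison and its error rate in a trial with an uneven split.

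**Working it through.** **Inputs.** Margin 250 ml (5.2). One-sided alpha 0.025, SD 236 ml (pilot) or 330 ml (conservative), and conservative true difference 400 ml (7.1.1). Completers N = 19 (6.3.1). Mean pilot control UF 162 ml (3.8). The period effect π is not in the document; 25, 50 and 100 ml are assumed. Against 162 ml, 50 ml is 31% and 100 ml is 62%.

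**The plan's own figure.** Section 7.1.1's printed formula gives (1.96 + 0.842)² × 236² / (2 × 324²) = 2.08, so 3, and (1.96 + 0.842)² × 330² / (2 × 150²) = 18.99, so 19. Both reproduce. The 2 in the denominator does not belong to a paired t-test on N subjects: with 19 subjects, SD 330 and a difference of 400 ml, that test has 46.6% power, not 80%. This is a separate matter, mentioned only because it explains the power levels below.

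**Algebra.** Let τ be the treatment effect and π the shift from period 1 to period 2. The expected difference (device minus control) is τ + π for control-first subjects (n1) and τ − π for device-first subjects (n2). For the pooled analysis:

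- mean = τ + π(n1 − n2)/N
- expected variance = σ² + 4π²n1n2/[N(N − 1)], which is σ² + π²N/(N − 1) when n1 = n2

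Half the sum of the two sequence means has expectation τ at any split, and its error uses only the within-sequence SD, on N − 2 degrees of freedom.

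**Bias, N = 19.** 11:8: 50 × 3/19 = 7.9 ml; 100 × 3/19 = 15.8 ml. 12:7: 50 × 5/19 = 13.2 ml; 100 × 5/19 = 26.3 ml.

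**Variance at equal counts.** At 10:10 with π = 100: 330² + 100² × 20/19 = 119,426, so the SD is 346 ml instead of 330. Simulated power at 400 ml is 45.1% pooled and 48.6% adjusted.

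**Type I error given the split** (400,000 simulated trials per setting, N = 19, SD 330). The two figures are for a larger sequence that favours or disfavours the device:

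| Split | π = 50 | π = 100 | Adjusted |
|---|---|---|---|
| 10:9 | 2.6% / 2.2% | 2.4% / 1.8% | 2.5% |
| 11:8 | 3.0% / 1.9% | 3.3% / 1.3% | 2.5% |
| 12:7 | 3.5% / 1.6% | 4.4% / 0.9% | 2.5% |

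At SD 236, π = 100 and 12:7 the figures are 4.9% / 0.5%.

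**How often each split arises.** Assume 25 randomised in blocks of four within two dose strata of 5 to 20 subjects, 6 lost at random regardless of sequence, and no replacement. Then 10:9 occurs in 60%, 11:8 in 31%, 12:7 in 8% and 13:6 in 0.8%.

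**Type I error averaged over these splits.** At SD 330 and π = 100, with the two directions averaged (13:6 is 5.7% / 0.6%): 0.60 × 2.09 + 0.31 × 2.26 + 0.08 × 2.65 + 0.008 × 3.19 = 2.2%. At π = 50 it is 2.4%. At SD 236 it is 2.4% (π = 50) and 1.9% (π = 100). Adjusted it is 2.5%.

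**Power averaged over the splits, true difference 400 ml, pooled v adjusted** (200,000 simulated trials per setting):

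| π (ml) | SD 236 | SD 330 |
|---|---|---|
| 0 | 74.6 v 73.6 | 46.6 v 45.7 |
| 25 | 74.1 v 73.5 | 46.5 v 45.9 |
| 50 | 72.9 v 73.5 | 45.6 v 45.7 |
| 100 | 68.1 v 73.5 | 43.2 v 45.9 |

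The two tests break even at π of about 40 to 50 ml. At 10:9 with π = 100, the average 95% CI half-width is 122 v 113 ml (SD 236) and 164 v 158 ml (SD 330).

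**The case against.** The planned test is valid on average. With loss unrelated to sequence, the estimate is unbiased over the randomisation and the average type I error is below 2.5%. The 4.4% figure needs a 12:7 split (8% of trials), the device-favouring direction (about half of those) and a period effect of 100 ml. Even then the bias is 26 ml against a standard error of 330/√19 = 76 ml, or 0.35 standard errors. Below 40 to 50 ml, adjustment loses a little power. At the pilot difference of 574 ml and a 10:9 split, both tests have about 98% power (SD 330) or more than 99.9% (SD 236), even at π = 100.

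The evidence for a large period effect on this endpoint is also thin. Residual renal function is urinary. The study in section 3.7 describes variation between participants, not drift. Prescription changes may damp drift as well as cause it. The control dwell is held at 2.27% and 5 hours, on the same weekday and at the same time of day, with the periods only four to five weeks apart. N may exceed 19, since one evaluable treatment per arm is enough for inclusion, and withdrawn subjects may be replaced. The sample-size formula costs far more power than this does.

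All of this stands as a limit on size. It does not give a reason to discard the randomised factor. The average level hides error rates that differ from 2.5% in the trial actually run, and about 40% of trials would be 11:8 or worse under the assumptions above. Nor can this be left to a later document, because the protocol itself fixes both the test and the pooling.

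**Conclusion.** The concern holds as a change that should be made; it does not invalidate the trial. The algebra is exact for an additive period effect. Its size rests on an assumed π. For π of 50 to 100 ml and N = 19, the bias is 8 to 16 ml at 11:8 and 13 to 26 ml at 12:7. The level is exceeded over repeated trials only if loss is unbalanced by sequence in the direction that favours the device. Otherwise the cost is power when π exceeds about 50 ml (2.7 points at SD 330 and 5.4 at SD 236 for π = 100), together with a biased estimate in a trial with an uneven split. Pooling the two doses does not bias the average difference and is not at fault. The mismatch between the rejection rule in section 5.2 and the test in section 7.1.6 needs no assumption about π and must be settled in any case.

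**What to change.** In section 7.1.6, keep the doses pooled for the single primary contrast, but estimate it from a linear model of each subject's mean difference with sequence coded +1/2 and −1/2. The intercept is then the equal-weight mean of the two sequence means. Centring sequence at its sample mean would return the pooled estimate and must be avoided. A crossover model with subject, period and treatment is equivalent. Dose stratum may be added as a covariate centred at the observed dose mix, for precision only. Test the intercept against 250 ml at one-sided 0.025 with the model's degrees of freedom.

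Use the same model for sodium removal and glucose UF efficiency. Rewrite the rejection rule in section 5.2 to match, including its standard error, its degrees of freedom and its inequality, which points the wrong way for the stated alternative. Report the pooled t-test as a sensitivity analysis.

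The cost is wording and one degree of freedom (two with dose). With no period effect the power loss is about 0.4 points at 10:9, 1 at 11:8 and 3 at 12:7, or about 1 point averaged over the expected splits.

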### 7.1.7 Statistical analysis of secondary endpoint

For the secondary endpoints no. 2 (peritoneal sodium removal) and no. 3 (glucose UF efficiency), each subject is expected to have two efficacy evaluations treatments per study arm. Subjects with one or more evaluation treatment in each arm will be included in the secondary endpoint analysis. For all secondary endpoints, excluded subjects will be tabulated with narratives as to why they are excluded. A subject may be excluded for one or more secondary endpoints, that is, exclusions are made independently for each endpoint.

#### 7.1.7.1 AE and SAE rates

All safety events reported during the clinical investigation from either arm during the home treatment phase will add information to the safety dataset. Based on all safety data gathered during the study for the intent-to-treat (ITT) dataset, AE and SAE occurrences adjudicated to the Carry Life® UF treatment or the control treatment will be collected and summarized. The rates of AE and SAE and the rates of different types of AE and SAE during the Carry Life® UF treatment arm and during the control arm will be presented (events per day). Data for the home treatment phase per protocol (PP) data set and the in-clinic treatments will also be gathered and presented. The occurrence of AE and SAE for each Carry Life® UF glucose dose will be summarized.

#### 7.1.7.2 Peritoneal sodium removal

Based on data gathered from the efficacy evaluation treatments during the home treatment phase of the study, peritoneal sodium removal will be calculated. For each patient the average sodium removal from the per protocol efficacy evaluation treatments in each arm will be used for the analysis. A paired comparison between sodium removal achieved with the Carry Life treatment ( $NaRev_{CL}$ ) and sodium removal from the control CAPD dwell ( $NaRev_{CAPD}$ ) will be conducted. The average paired difference and the associated 95% CI will be calculated. Further, a t-test will be used to demonstrate that the Carry Life® UF treatment has a larger peritoneal sodium removal than the control 2.27% CAPD dwell. The analysis will be performed for both the ITT and the PP population. The difference in peritoneal sodium removal for each Carry Life® UF glucose dose and each fill volume compared to the control CAPD dwell will be summarized.

